5.13. Clinical Safety Assessments

5.13.1. Clinical Laboratory Evaluations

Clinical laboratory evaluations will be collected at Screening, Day 1, Week 2 visit, Week 4 visit, Week 12 visit, and at the Follow-Up Visit as described in [Appendix D](#).

5.13.2. 12-Lead Electrocardiograms

A 12-lead ECG, including ECG parameters of RR, PR, QRS, QT and QTc intervals as well as significant findings will be obtained at Screening, Week 4 visit, and at the Follow-Up Visit.

When 12-lead ECGs are scheduled at the same time as blood draws, the order of evaluation will be ECG, vital signs, and then blood draw.

5.13.3. Vital Signs

Heart rate, blood pressure, and respiratory rate (measured after the patient has been resting and seated for at least 3 minutes), will be obtained at every visit. Temperature will also be obtained at the Screening visit. Height is obtained only at the screening visit. Weight will be obtained at each visit; and BMI will be calculated at screening and subsequent visits.

When vital signs are scheduled at the same time as blood draws, the order of evaluation will be ECG, vital signs, and then blood draw.

5.13.4. AE Assessments

Patients will be asked how they are feeling from the first administration of study drug through the Follow-Up visit (see [Section 7.2](#)). Patients will also be encouraged to voluntarily report any AEs they experience during the study.

5.13.5. Physical Examinations

A routine physical examination will be performed at Screening, and an abbreviated physical examination (consisting of an examination of general appearance, skin, lungs, cardiovascular and abdomen) will be performed at the Follow-Up Visit.

5.13.6. Neurological Examinations

A neurological examination will be administered at Screening and at the Follow-Up Visit as described in the Study Manual.

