1.3. Overview of CK-2127107 Clinical Studies

Phase 1 Studies

CK-2127107 has been evaluated in five Phase 1 studies.

In a "first in human" study conducted in 35 healthy men (Study CY 5011), single oral doses of a SDD suspension (CK-2127107 ranging from 30 to 4000 mg were all well tolerated and no maximum tolerated dose was established.

In Study CY 5012, multiple dose administration of the CK-2127107 SDD suspension at 300 and 500 mg twice daily for either 10 or 17 days was well tolerated by 59 young and elderly healthy subjects and allowed the steady-state PK profile to be described.

A 4-way crossover, single dose PK/pharmacodynamic (PD) study (Study CY 5013) performed with placebo, 300 mg, 1000 mg and 3000 mg of the CK-2127107 SDD suspension demonstrated a dose- and concentration-dependent increase in the force-frequency relationship of the tibialis anterior muscle with transcutaneous electric stimulation of the deep fibular nerve.

Another study in 25 healthy men (Study CY 5014) was conducted to evaluate the relative oral bioavailability of a suspension of the crystalline form of CK-2127107, CK-2127107 active pharmaceutical ingredient (API), to the CK-2127107 SDD suspension dosed at 300 and 1000 mg.

Lastly, in Study CY 5015, the PK of a tablet formulated with CK-2127107 API was compared to CK-2127107 API suspension and found to have adequate bioavailability for use in future studies. The food effect of the tablet was also evaluated in Study CY 5015.

The terminal half-life ($t_{1/2}$) of CK-2127107 was generally around 12 hours with a time to maximum concentration (t_{max}) of 2-3 hours. The increase in exposure was largely dose-proportional although exposure was more variable at doses ≥ 3000 mg. There were no observed differences in PK parameters between young and elderly subjects but mean exposure was

slightly higher in women vs. men. A food effect was demonstrated with 2.6- and 1.6-fold increases in C_{max} and AUC_{∞} , respectively, following administration of the tablet formulation (500 mg as 2 x 250 mg tablets) with a high fat meal.

Exposure (C_{max} and AUC) to the inactive metabolite, CK-2127106, was higher after multiple doses of CK-2127107 compared to single doses. The geometric mean half-life of CK-2127106 ranged from 25.4 to 39.3 hours. Maximum concentrations (C_{max}) and area under the concentration-time curve (AUC) values increased somewhat greater than dose-proportionally following multiple dosing.

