5.7. Follow-Up Visit

The following procedures will be performed at a Follow-Up Visit 4 weeks after each patient's final dose of study drug:

1. 12-lead ECG

2. Vital signs including heart rate, blood pressure, and respiratory rate measured after the patient has been resting for at least 3 minutes
3. Weight and calculation of BMI
4. Abbreviated physical examination
5. Neurological examination
6. Clinical laboratory evaluations, including CBC and WBC with differential, serum chemistries, cystatin C, UA, and TSH
7. Pregnancy test for all females of childbearing potential

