8.3.2. Safety Endpoints

The safety endpoints are listed in the following:

- The incidence and severity of TEAEs
- Clinically important changes in safety assessment results [including, as appropriate, vital signs, clinical laboratory tests, ECGs, Ashworth score, falls assessment, physical and neurological examinations, BDI-Fast Screen and suicidality assessment].

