8.8. Neurological Examinations

A neurological examination will be administered at Screening and Follow-Up Visits. Neurological examination findings will be summarized for eye movements, facial sensations, motor function strength, sensory, reflexes, plantar response, cerebellar function / coordination by

visit, dose level and overall. Neurological examination findings shift from baseline visit to post-baseline visit will also be tabulated.

Individual neurological examination findings will be listed for each test chronologically by patient ID, visit, and the actual assessment date and time.

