APPENDIX B. ANALYSIS VISIT WINDOWS

Analysis Visit Windows for SVC, Muscle Strength, ALSFRS-R, Voice Recording, Fine Motor Skills, ALSAQ-5, Vital Sign, Ashworth Scale and BDI-Fast Screen

Visit	Scheduled Day	Lower Bound	Upper Bound
Screening	<1	<1	<1
Day 1	1	1	1
Week 2	15	2	21
Week 4	29	22	42
Week 8	57	43	70
Week 12	85	71	98
Follow-up	113	99	> 99

Analysis Visit Windows for 12-lead ECG

Visit	Scheduled Day	Lower Bound	Upper Bound
Screening	<1	<1	<1
Week 4	29	1	70
Follow-up	113	71	>71

Analysis Visit Windows for Clinical Safety Laboratories

Visit	Scheduled Day	Lower Bound	Upper Bound
Screening	<1	<1	<1
Day 1	1	1	1
Week 2	15	2	21
Week 4	29	22	56
Week 12	85	57	98
Follow-up	113	99	>99

Analysis Visit Windows for PK Concentration

Visit	Scheduled Day	Lower Bound	Upper Bound
Day 1	1	1	1
Week 2	15	2	21
Week 4	29	22	42
Week 8	57	43	70
Week 12	85	71	>71

Analysis Visit Windows for Neurological Exam

Visit	Scheduled Day	Lower Bound	Upper Bound
Screening	<1	<1	<1
Follow-up	113	1	>99

Analysis Visit Windows for SVC Assessed at Home

Visit	Scheduled Day	Lower Bound	Upper Bound
Day 1	1	1	1
Week 1	8	2	11
Week 2	15	12	18
Week 3	22	19	25
Week 4	29	26	32
Week 5	36	33	39
Week 6	43	40	46
Week 7	50	47	53
Week 8	57	54	60
Week 9	64	61	67
Week 10	71	68	74
Week 11	78	75	81
Week 12	85	82	88
Week 13	92	89	95
Week 14	99	96	102
Week 15	106	103	109
Week 16	113	110	>110

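### In completers the only post-baseline neurological examination is about 28 days off drug, and the SAP's single window replaces early stoppers' near-drug examination with another off-drug one

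*Protocol*

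**What the plan says.** **Endpoint.** Protocol 8.3.2 lists as a safety endpoint "Clinically important changes in safety assessment results", and names physical and neurological examinations among the assessments. SAP 2.2.5 repeats this.

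**Schedule.** For the neurological examination, Protocol 5.13.6 states: "A neurological examination will be administered at Screening and at the Follow-Up Visit as described in the Study Manual". SAP 8.8 agrees: "A neurological examination will be administered at Screening and Follow-Up Visits". For the physical examination, Protocol 5.13.5 begins "A routine physical examination will be performed at Screening, and an abbreviated physical examination" and places the abbreviated one at Follow-Up. The visit lists in Protocol 5.2 to 5.6 and both schedules of events show neither examination at Day 1 or at Weeks 2, 4, 8 or 12.

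**Timing of Follow-Up.** Protocol 5.7 opens "The following procedures will be performed at a Follow-Up Visit 4 weeks after each" patient's final dose. Table 2 of the Protocol allows ± 4 days.

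**Early stoppers.** Protocol 5.8 adds neurological and abbreviated physical examinations at an Early Termination Visit, held as soon as possible after drug is stopped. Protocol 5.15 asks these patients to attend Follow-Up 28 days after the last dose as well.

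**Analysis.** SAP 8.8 provides a summary by visit and a shift table ("Neurological examination findings shift from baseline visit" to post-baseline). It covers eye movements, facial sensation, motor strength, sensory findings, reflexes, plantar response and cerebellar function or coordination. In SAP Appendix B, the table headed "Analysis Visit Windows for Neurological Exam" has one post-baseline row, labelled Follow-up, running from Day 1 to >99. Under SAP 5.5.5 a scheduled visit takes priority within a window, and only the selected record is tabulated.

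**The concern.** A safety shift table is normally read as a comparison of patients before and during treatment. For completers this one compares a pre-dose examination with one made after the drug has gone. If the arms look alike, a reader of the study report may take that as reassurance about neurological signs on drug, which the table cannot give for any effect that reverses within the four weeks off drug.

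The gap is specific to the two examinations. The other assessments named in the same endpoint (vital signs, laboratory tests, Ashworth, falls, BDI-Fast Screen) have scheduled on-drug measurements, and the ECG has Week 4. Protocol 3.2 describes this as the first study of the drug in ALS. Multiple dosing in the completed Phase 1 studies (Protocol 1.3) lasted 10 or 17 days, against 12 weeks here.

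The examinations made closest to drug are those at Early Termination, and patients who stopped because of an adverse event are among those examined. The window rule removes these examinations from the table whenever the patient also does as asked and attends Follow-Up.

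**Working it through.** The plan states no figure on this point, so there is none to reproduce. The check has three parts.

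**1. How far off drug is the Follow-Up examination?**
Inputs:
- Parent half-life: Protocol 1.3, "of CK-2127107 was generally around 12 hours".
- Inactive metabolite half-life: 25.4 to 39.3 hours, same section.
- Follow-Up at 28 ± 4 days after the last dose: Protocol 5.9, Table 2.

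Formulas: half-lives elapsed = days × 24 / half-life; residual fraction = 2^(−half-lives), assuming first-order elimination.

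| Days since last dose | Parent (12 h): half-lives; residual | Metabolite (39.3 h): half-lives; residual |
|---|---|---|
| 24 | 576/12 = 48; 3.6e-15 | 576/39.3 = 14.7; 3.9e-5 |
| 28 | 672/12 = 56; 1.4e-17 | 672/39.3 = 17.1; 7.1e-6 |
| 32 | 768/12 = 64; 5.4e-20 | 768/39.3 = 19.5; 1.3e-6 |

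At 25.4 hours the metabolite figures are 22.7, 26.5 and 30.2 half-lives. Exposure is effectively nil throughout the window.

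**2. Who is affected?**
Protocol 8.1.2 assumes 10% dropout: 445 × 0.9 = 400.5, so about 400 patients complete dosing. Scheduled on-drug neurological or physical examinations for each of them: 0.

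**3. What does the window rule do to an early stopper?**
Take, as an illustration only, a last dose on Day 40, Early Termination on Day 42 and Follow-Up on Day 40 + 28 = 68. Both examinations fall in the window from Day 1 to >99.
- SAP 5.5.5, first rule: the scheduled visit is used, so Day 68 is tabulated.
- If the early Follow-Up were not counted as scheduled, the next rule takes the record nearest to the scheduled day, Day 113: |68 − 113| = 45 against |42 − 113| = 71. Day 68 is selected again.
- This is general. With a last dose before Day 85, a Follow-Up 28 days later falls before Day 113 and is nearer to it than any Early Termination Visit that preceded it.
- If this patient does not attend Follow-Up, the Day 42 examination enters the row labelled Follow-up. One row then mixes near-drug and off-drug examinations.

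An Early Termination examination is near drug only if it is prompt. The parent residual is 2^(−2) = 25% at 1 day, 2^(−4) = 6.25% at 2 days, 2^(−6) = 1.6% at 3 days and 2^(−14) = 0.006% at 7 days.

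**The case against.** The strongest reply is that the trial does look at patients on drug. Protocol 3.1 has them evaluated at every visit for signs and symptoms of intolerance. Adverse events are asked about at each visit, and the definition in Protocol 7.1.1 includes signs. Falls are assessed from Day 1. Ashworth, dynamometry, ALSFRS-R and the tracing tasks are done at every visit. **This stands.** A reader might infer that reversible neurological effects cannot be detected anywhere in the trial; the documents do not support that. What remains is narrower. No listed on-treatment assessment formally covers reflexes, sensation, plantar response, eye movements or cerebellar function. Protocol 7.3.1 also keeps expected signs of ALS progression (Table 5 includes gait disturbance, dysarthria and muscle weakness) out of adverse event collection unless serious, so that route is partly closed.

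Other replies that stand:
- A reader might infer that the shift table must look the same across arms whatever the drug does. Persistent or slowly reversing effects could still appear at Follow-Up, and looking for them is a sound reason for an off-drug exit examination.
- No data are lost. SAP 5.5.5 and 8.8 keep the displaced records in listings.
- The displacement concerns the neurological examination only. SAP 8.7 sends clinically significant physical findings to Medical History or Adverse Events, and Appendix B has no physical examination window.
- Dose-related dizziness in Phase 1 might be cited to raise the stakes. Protocol 1.3 puts the increase at 2250 mg and above, and the highest dose here is 450 mg twice daily, so it adds little.
- The Protocol and SAP agree on when the examinations take place. This is a design and tabulation point, not a contradiction.

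**Conclusion.** The point holds within limits. For completers, about 400 of 445 on the plan's own figures, the neurological shift table compares Screening with an examination 24 to 32 days after the last dose (48 to 64 parent half-lives). It cannot show effects that reverse within about four weeks. For early stoppers who attend both visits, the window and priority rules remove the more informative neurological examination from the table.

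The number of patients in the second group cannot be derived. Treating the 10% dropout (about 45 patients) as that number is tempting but unsupported. Protocol 5.15 encourages patients who stop drug to keep attending, so dropouts and drug stoppers differ, and some early leavers give only telephone data without an examination.

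The conclusion assumes that the half-life in ALS patients resembles the Phase 1 figure; with 48 half-lives at the earliest visit, a several-fold error would not change it. It also assumes that the Study Manual, which is not among the documents, adds no examination visits. No efficacy conclusion is affected. The SAP change is worth making because it costs almost nothing and prevents a misreading.

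**What to change.** **SAP change.**
- In Appendix B, replace the single post-baseline neurological window with two: Early Termination and Follow-up. Assign them by the nominal visit on the eCRF, because Early Termination can fall on any day and day bounds cannot separate the two. Adjust SAP 5.5.4, which now places early discontinuation visits by day bounds.
- In SAP 8.8, tabulate the Early Termination examination in its own row of the summary and shift tables, so that the Follow-Up record neither displaces it nor shares a row with it.
- Add a footnote that post-baseline results in completers were obtained about 28 days after the last dose.

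**Cost.** This is a short SAP revision before database lock and one extra row, with no new procedure and no protocol amendment. The downside is that the row will hold a small, self-selected group of early stoppers, so it should be read descriptively, by arm, without inference. Under the current Protocol it cannot include completers.

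**Optional design point for the sponsor.** Scheduling an examination at Week 12 would close the gap in completers. Moving it there gives up their only off-drug exit examination, and adding it brings a further procedure; either needs a protocol amendment. It also comes late for this trial: the SAP, dated December 2018, already lists FAS patients by site in Appendix C (20 + 53 + 49 + 52 + 61 + 71 + 51 + 36 + 65 = 458, where 36 is the sum of the site counts in pool 8).

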5.13.7. Beck Depression Inventory-Fast Screen (BDI-Fast Screen)

The BDI-Fast Screen will be assessed at all study visits as described in the Study Manual.

5.13.8. Falls Assessment

Falls assessment will be performed at each study visit except Screening as described in the Study Manual.

5.13.9. Ashworth Scale

The Ashworth scale to assess spasticity will be performed at each study visit. Further description of the Ashworth Scale can be found in the Study Manual.

5.14. Clinical and Pharmacodynamic Outcome Measures

5.14.1. Pulmonary Function Assessment

The pulmonary function assessment in this study will be SVC. Pulmonary function assessment will be performed at each study visit as described in the Study Manual. Patients will also perform home SVC assessments weekly through the course of the study following Day 1 (if the device is suitable for use in that region) as described in the Study Manual.

5.14.2. Hand-Held Dynamometry

Muscle strength measurements of selected muscles will be performed using HHD and hand grip dynamometry at each study visit as described in the Study Manual.

5.14.3. ALSFRS-R

The ALSFRS-R will be performed at each study visit as described in the Study Manual.

5.14.4. Voice Recording

Voice recording will be performed at each study visit and for patients who have access to mobile devices weekly at home as described in the Study Manual.

5.14.5. Fine Motor Assessments (Handwriting and Figure Tracing)

The handwriting and figure tracing assessments will be done at each study visit (if the device is suitable for use in that region) as described in the Study Manual.

5.14.6. ALSAQ-5

The ALSAQ-5 will be performed at each study visit as described in the Study Manual.

5.14.7. Health Economic Outcomes Measures

During the course of the study, if the patient is prescribed and agrees to receive any of the following, it will be recorded including the date prescribed:

- Non-invasive ventilation
- Gastrostomy tube
- Manual wheelchair
- Power wheelchair
- Augmentative and alternative communication

5.15. Removal of Patients from Study Participation

Patients will be informed that they are free to discontinue study drug or withdraw from the study at any time and for any reason. The Investigator may discontinue study drug or withdraw a patient from the study if, in the Investigator's opinion, it is not in the best interest of the patient to continue the study. Patients may discontinue study drug or withdraw from the study due to the following:

- a. A change in compliance with inclusion/exclusion criteria that is clinically relevant and/or affects patient safety, and/or study assessments/objectives, etc.
- b. Occurrence of intolerable AEs
- c. Changes in vital signs, ECGs, or clinical laboratory results that, in the opinion of the Investigator, pose a significant health risk
- d. Intake of non-permitted concomitant medication that might affect patient safety or study assessments/objectives, etc.

- e. eGFR calculated using the CKD-EPI cystatin equation (Inker, Schmid et al. 2012) shows a >25% decline compared to baseline (defined as Day 1 or Screening if Day 1 value is not available) as long as the decline is not related to dehydration or a superimposed reversible process such as infection or nausea.
- f. Changes in liver function tests (LFTs) as outlined in [Appendix C](#)
- g. Receiving any form of stem cell therapy for ALS either as part of a clinical trial or outside of a clinical trial
- h. Having a diaphragmatic pacing system implanted either as part of a clinical trial or outside of a clinical trial
- i. Initiating edaravone after screening.
- j. Initiating riluzole after screening.
- k. Initiating gene therapy for ALS either as part of a clinical trial or outside of a clinical trial after screening.

Patients should be strongly encouraged to perform the early termination visit as soon as possible following last dose of study drug taken, and the Follow-Up Visit should be performed 28 days after last dose taken of study medication. In addition, they should be encouraged to return for all remaining study visits and assessments (with the exception of 12-lead ECG, clinical laboratory and PK sampling) for the duration of the study following study drug discontinuation. These remaining study visits should be performed according to the original study visit windows.

Patients who decide to start or stop edaravone or riluzole after screening and before randomization, will no longer be eligible to be randomized and should not be followed subsequently. If a patient decides to start edaravone or riluzole after randomization, they will be terminated from taking study medication once that is known by the site. They should return to the clinic for their early drug termination visit as soon as possible following last dose of study drug taken and return 28 days after last dose taken for the Follow-Up Visit. They will not be followed thereafter.

For patients who terminate early from the study and do not want to return to the clinic for the visits as described in the above paragraph, phone call visits should be performed to collect the information if the patient is willing (see [Section 5.8](#)).

Notification of discontinuation will immediately be made to the Sponsor's Medical Monitor. In case of withdrawal of study participation, efforts will be made to perform Early Termination ([Section 5.8](#)) and Follow-Up visit assessments ([Section 5.7](#)). The date the patient is withdrawn from the study and the reason for discontinuation will be recorded on the patient's eCRF. All patients who prematurely discontinue from the study for AEs will be followed for up to 30 days, until the AE resolves, or until the unresolved AE is judged by the Investigator to have stabilized.

The primary reason for a patient prematurely withdrawing from the study should be selected from the following categories and documented in the source documents:

- a. Patient Death
- b. Adverse Event: One or more clinical or laboratory events which, in the medical judgment of the Investigator, are grounds for discontinuation even if the event does not appear to be related to study medication. The patient may withdraw because of an AE even if the Investigator does not feel that the event is grounds for discontinuation.
- c. Protocol Violation: The patient's findings or conduct failed to meet the protocol entry criteria or failed to adhere to the protocol requirements

- d. Patient Withdrawal of Consent: Patient desires to withdraw from further participation in the study and reason for doing so.
- e. Administrative/Other: Any cause of premature termination from the study other than the above, such as illness of investigator, loss of study drug, or termination of study by the Sponsor.

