5.6. Handling of Missing Data

5.6.1. Missing Efficacy Endpoints

The efficacy analysis will be performed using mixed effect model as specified. The model will provide unbiased results without imputation assuming that the missing patterns are missing at random (MAR). If the percentage of missing values in the primary efficacy endpoint is > 20%, sensitivity analyses assuming different missing data pattern will be conducted. Multiple imputation within the dose group of each missing data pattern will be performed using Markov chain Monte Carlo method.

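### Protocol 5.15 contradicts itself on follow-up of patients who start edaravone or riluzole after randomisation, and its specific rule leaves earlier starters with no Week 12 SVC value

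*Protocol*

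**What the plan says.** Protocol 5.15 lists reasons, a to k, for which a patient may stop study drug or withdraw. Item i is "Initiating edaravone after screening" and item j is the same for riluzole. Items g, h and k cover stem cell therapy, a diaphragmatic pacing system and gene therapy. The text after the list asks for an early termination visit and a Follow-Up Visit. It adds that "they should be encouraged to return for all remaining study visits and assessments", apart from ECG, laboratory and PK sampling, and "These remaining study visits should be performed according to the original study visit windows". Nothing there exempts items i and j.

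A later paragraph of the same section deals only with patients who start edaravone or riluzole after randomisation. They are taken off study drug once the site knows, have an early termination visit, and "return 28 days after last dose taken for the Follow-Up Visit". Then: "They will not be followed thereafter".

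SAP 5.6.1 relies on missing at random (MAR) for the mixed-model efficacy analyses, and adds imputation by missing-data pattern only if more than 20% of primary endpoint values are missing. SAP 7.5.2 plans, without any such condition, a missing-not-at-random (MNAR) sensitivity analysis that imputes missing values in all groups from observed placebo data. The SAP has no rule for patients who start either drug, or for data collected after the start.

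**The concern.** One paragraph encourages these patients to attend through Week 12, and the other ends their follow-up 28 days after last dose. A site cannot do both. If the specific paragraph governs, whether a Week 12 SVC value exists depends on why study drug was stopped. A patient who receives gene therapy, stem cell therapy or a pacing system is encouraged to return; one who starts riluzole is not. The protocol gives no reason for the difference.

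A patient who adds an ALS drug mid-trial may be doing so because of perceived progression. The lost values could then be worse than the model predicts, and the loss could differ between arms. Values that are collected can be left out of an analysis later, but values never collected cannot be recovered.

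**Working it through.** **1. Which starters lose Week 12.** Inputs: Protocol 5.7 and 5.8 (SVC is measured at both the Follow-Up and the early termination visit), SAP 5.5.4 and SAP Appendix B.

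- Early termination visits are assigned by study day. Day 43-70 maps to Week 8 and Day 71-98 to Week 12.
- Scheduled visits are assigned by nominal visit. With a last dose on Day 43-70, the Follow-Up Visit nominally falls on Day 71-98 (43 + 28 = 71; 70 + 28 = 98). That is inside the Week 12 day bounds, but the record is still labelled Follow-Up and does not fill Week 12.
- So only an early termination visit on Day 71 or later supplies the primary value. Starting in roughly the first 70 of 84 dosing days leaves it missing by rule.

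**2. The plan's own power.** Inputs from Protocol 8.1.2: contrast (-5, -1, 3, 3), advantages over placebo of 0, 2.75, 5.5 and 5.5, SD 14, two-sided alpha 0.05, 445 randomised, 10% dropout.

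- Contrast value L = -2.75 + 16.5 + 16.5 = 30.25.
- Sum of squared coefficients = 25 + 1 + 9 + 9 = 44.
- With n = 100 per arm, SE = 14 × √(44/100) = 9.29 and L/SE = 3.257.
- Power = Φ(3.257 - 1.960) = 90.3%. The stated 90% is reproduced.
- Dividing the coefficients by 6, as the SAP code does, gives a planned contrast of 30.25/6 = 5.04 with SE 9.29/6 = 1.55.

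**3. Power with starters.** The documents give no start rate, so 1-5% of randomised patients is assumed. Evaluable N is 445 × (0.90 - x) if starters are lost in addition to the 10%. If they are already inside the 10% and are then followed to Week 12, it is 445 × (0.90 + x).

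| Start rate x | Lost in addition: N, power | Inside the 10%, then followed: N, power |
|---|---|---|
| 1% | 396, 90.0% | 405, 90.6% |
| 2% | 392, 89.7% | 409, 90.9% |
| 5% | 378, 88.6% | 423, 91.8% |

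**4. Bias on the scaled contrast.** Weights w = (-5/6, -1/6, 1/2, 1/2). Assume lost patients are d = 5 points worse at Week 12 than MAR predicts. An arm that loses a fraction f then has its mean overstated by f × d, and bias = Σ w × f × d.

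| Loss in placebo / 300 / 600 / 900 mg/day | Bias (points) |
|---|---|
| 5 / 5 / 5 / 5% | 0 |
| 5 / 5 / 2 / 2% | -0.208 - 0.042 + 0.05 + 0.05 = -0.15 |
| 10 / 5 / 0 / 0% | -0.417 - 0.042 = -0.46 |
| 0 / 0 / 5 / 10% | 0.125 + 0.25 = +0.38 |

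Average loss in these rows is 3.5-5%, inside the assumed range. The largest bias is 0.46/1.55, about 0.3 of a standard error.

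**5. Whether the planned sensitivity analyses repair it.** The pattern imputation in SAP 5.6.1 needs more than 20% missing; 10% dropout plus 5% starters is 15%. The analysis in SAP 7.5.2 imputes placebo starters from observed placebo patients. If placebo starters progress faster than those observed, it does not capture that.

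**The case against.** The strongest case for the rule is that SVC measured after another ALS drug is started is confounded by that drug. Ending collection would fit a question about effect without new background therapy. This stands as an argument about how the data are used, not about whether to collect them. It also does not explain why patients who start gene or stem cell therapy are encouraged to return.

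Several stronger readings are tempting, and the documents do not support them:

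- A reader might infer that every other discontinuer is followed to Week 12. The others are only encouraged to return, and Protocol 7.7 makes pregnancy a further exception.
- A reader might infer that starters are dropped at once, or always lose both Week 8 and Week 12. They have two further SVC measurements. An early termination visit can fill the Week 8 or Week 12 window, and their earlier values inform the MAR prediction.
- A reader might infer that MAR goes untested. SAP 7.5.2 is an unconditional MNAR analysis, and SAP 7.9.1 adds an exploratory joint rank test on SVC that compares early discontinuers at the last shared time point. Both soften the problem without removing it.
- A reader might infer that the missingness is shown to be informative, or that it flatters the drug. The documents hold no data on who starts or why. If lack of effect drives starting on placebo, the bias is conservative.
- A reader might infer that power is certainly reduced. The 10% dropout may already include starters.

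Inclusion criteria 11 and 12 exclude patients who plan to start either drug, which limits the rate.

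**Conclusion.** The contradiction within Protocol 5.15 is established by the text. So is its consequence under the specific rule: a starter whose early termination visit falls before Day 71 has no Week 12 SVC value. That the loss is informative is a plausible judgement, not a documented fact.

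The size is unknown because no start rate is given. Under the assumed 1-5%, power is at worst about 88.6% against 90.3%, and it is not reduced if starters are within the 10%. With a 5-point shortfall, bias is zero for equal loss, -0.15 to -0.46 if placebo and the low dose lose more, and about +0.38 if the high doses lose more, against a planned contrast of 5.04. This does not threaten the primary result. It is a cheap improvement that removes a contradiction and an avoidable source of missing data. No view is taken on the rule for stopping study drug.

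**What to change.** Reconcile the two paragraphs of Protocol 5.15 so that patients who start edaravone or riluzole after randomisation are also encouraged to attend the remaining scheduled efficacy visits through Week 12, and record the start date. In the SAP, state whether data after the start enter the primary MMRM, run the other option as a sensitivity analysis, and report the number of starters by arm.

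The cost is up to three already scheduled visits (Weeks 4, 8 and 12) for a few patients, plus flagging of data collected after the start. An early termination visit between Day 2 and Day 21 already counts as Week 2. The SAP, dated 14 December 2018, already tabulates full analysis set patients by site. If follow-up has ended, the protocol change comes too late for this trial. The SAP part can still be done before database lock: say how the missing Week 12 values of starters, and any data collected after the start, are handled.
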